3.8 Safety analyses

For all safety analyses, the safety analysis set will be used. All safety data will be listed and tables will be summarized by dose cohorts of Phase I and overall for Phase II.

The overall observation period will be divided into three mutually exclusive segments:

1. pre-treatment period: from day of patient's informed consent to the day before first dose of study medication
2. on-treatment period: from day of first dose of study medication to 30 days after last dose of study medication
3. post-treatment period: starting at day 30+1 after last dose of study medication.

3.8.1 Adverse events (AEs)

Adverse events will be assessed according to the Common Terminology Criteria for Adverse Events (CTCAE) version 4.03. If CTCAE grading does not exist for an adverse event, the severity of mild, moderate, severe, and life-threatening, corresponding to Grades 1 - 4, will be used. CTCAE Grade 5 (death) will not be used in this study; rather, information about deaths will be collected through the Study Evaluation Completion page. Adverse events will be coded using the most recent version of the medical dictionary for regulatory activities (MedDRA) available at the time of each analysis.

The AEs experienced by the patients in all the observation periods will be listed. The AEs reported in pre-treatment and post-treatment period will be flagged in the listing. In an AE listing, details will be provided for severity grade of AE, seriousness of AE, its relationship to

study treatment, its duration, action taken, outcome, and whether medication or therapy was given to patient.

Treatment Emergent AEs are those, which start in on-treatment period, or which start in pre-treatment period but worsen in on-treatment period. Summary tables for all TEAEs will be provided by study treatment group.

AEs will be summarized by number and percentage of subjects having at least one AE, having at least one AE in each primary system organ class (SOC) and for each preferred term (PT) using MedDRA coding. A subject with multiple occurrences of an AE will be counted only once in the respective AE category. A subject with multiple CTCAE grades for the same preferred term will be summarized under the maximum CTCAE grade recorded for the event. The tables will be summarized alphabetically by SOC and in decreasing frequency of PTs. The decreasing order of PTs will be based on the total count.

AE overview table will be provided with information on number and percentage of patients having any AE, any SAE, any Severe AE, any AE leading to discontinuation of study drug, dose adjustments and interruption, any fatal AE and deaths due to any cause. The incidences of all TEAEs will be summarized by the SOC and PT. In addition to this, the incidences of all grades of TEAE and of grades 3 and 4 TEAE will be summarized. Serious TEAEs including fatal and non-fatal AEs, Severe TEAEs, AEs with relationship to study treatment, AEs leading to discontinuation of any study treatment, AEs leading to dose adjustment or interruption, will also be summarized. All AEs will be summarized regardless of relationship to study treatment.

3.8.1.1 Adverse events of special interest / grouping of AEs

Not Applicable

3.8.2 Deaths

Separate summaries for on-treatment and all deaths (on-treatment and post-treatment) will be produced by study dose group, system organ class and preferred term. All deaths will be listed and post treatment deaths will be flagged.

3.8.4 Other safety data

3.8.4.1 ECG and cardiac imaging data

3.8.4.1.1 ECG data

12-lead ECGs including PR, QRS, QT, QTcF, and HR intervals will be obtained for each subject during the study. All ECG data will be listed, notable values will be flagged and any other information collected will be listed as appropriate. Triplicate ECGs, performed in case when QTcF prolongation of ≥ 480 msec is observed, will also be listed.

The following summaries will be provided by dose cohorts of Phase I and overall for Phase II:

- Change from baseline in QT intervals for each visit.
- The frequency and percentage of patients with notable ECGs and newly occurring qualitative ECG abnormalities.

Listing of ECG intervals will be provided, where ECG notable parameters will be flagged. Listing of ECG findings, cardiac imaging and QT prolonging concomitant medication will also be produced.

The overall assessment results will be summarized using frequency and percentages, for shifts from baseline to worst ECG value on treatment.

The number and percentage of subjects with notable ECG values will be presented by dose group. Notable abnormal values for ECG parameter will be listed and flagged.

QT, or QTcF

- New value of > 450 and ≤ 480 ms
- New value of > 480 and ≤ 500 ms
- New value of > 500 ms
- Increase from Baseline of > 30 ms to ≤ 60 ms
- Increase from Baseline of > 60 ms

HR

- Increase from baseline $> 25\%$ and to a value > 100 bpm
- Decrease from baseline $> 25\%$ and to a value < 50 bpm

PR

- Increase from baseline $> 25\%$ and to a value > 200 ms
- New value of > 200 ms

QRS

- Increase from baseline $> 25\%$ and to a value > 110 ms
- New values of QRS > 110 ms

3.8.4.1.2 Cardiac Imaging Data

Cardiac imaging results from MUGA Scan or ECHO, collected at screening will also be listed.

3.8.4.2 Vital signs

The vital sign parameters, sitting blood pressure, sitting pulse, respiratory rate, weight, height, BMI and body temperature, will be listed for each visit. Notable abnormal values will be flagged.

The vital sign value results will be summarized by dose cohort of Phase I and by group of Phase II as mentioned below:

- Change from baseline to worst value (descriptive statistics)
- Shift table from baseline to maximum value on-treatment value, for all vital sign parameters (frequency count and percentages)
- Clinically notable vital sign abnormalities (frequency count and percentages)

Notable abnormalities for vital sign values is as follows:

Table 3-7 Clinically notable elevated values

| Variable | Criteria |
|------------------|--|
| Systolic BP | ≥ 180 mmHg and an increase ≥ 20 mmHg from baseline |
| Diastolic BP | ≥ 105 mmHg and an increase ≥ 15 mmHg from baseline |
| Body temperature | $\geq 39.1^{\circ}\text{C}$ (102.3°F) |
| Weight | increase from baseline of $\geq 10\%$ |
| Heart rate | ≥ 120 bpm with increase from baseline of ≥ 15 bpm |

Table 3-8 Clinically notable below normal values

| Variable | Criteria |
|------------------|--|
| Systolic BP | ≤ 90 mmHg and a decrease ≥ 20 mmHg from baseline |
| Diastolic BP | ≤ 50 mmHg and a decrease ≥ 15 mmHg from baseline |
| Body temperature | $\leq 35^{\circ}\text{C}$ (95°F) |
| Weight | decrease from baseline of $\geq 10\%$ |
| Heart rate | < 50 bpm with decrease from baseline of ≥ 15 bpm |

3.8.4.3 Pregnancy Test

Pregnancy test results in serum and urine will be listed.

3.8.4.4 Physical Examination

The results of Physical examination at screening will be listed.

3.8.4.5 Tolerability

Tolerability of study drug treatment will be assessed by summarizing the number of treatment dose interruptions and dose change. Reasons for dose interruption and dose change will be listed by patient and summarized for Safety set, and will be presented by dose cohorts of Phase I by group of Phase II.

Cumulative dose, dose intensity and relative dose intensity of ribociclib, everolimus and exemestane will be listed by patient and summarized.

Categories for relative dose intensity for ribociclib, everolimus and exemestane will be specified as follows:

- <0.7
- $\geq 0.7 - <0.9$

- ≥0.9

The number and proportion of patients within each category will be presented.

3.9 Pharmacokinetic end points

Ribociclib and everolimus concentrations will be listed and summarized descriptively based on planned timepoints. The concentration data will be provided for all patients in PK analysis set.

Descriptive statistics will include mean, standard deviation, CV%, median, range. All PK parameters will be provided by dose group and study day. When a geometric mean is presented, it will be stated as such. Only median values and ranges will be given for T_{max} .

[figure not shown]
Descriptive graphical plots of individual plasma concentration by time will be generated for ribociclib (and LEQ803) and everolimus. Also mean concentration-time profiles will be generated for ribociclib (and LEQ803) and everolimus.

[figure not shown]
3.10 PD and PK/PD analyses

[figure not shown]
Not Applicable

[figure not shown]
3.11 Patient-reported outcomes

[figure not shown]
Not Applicable

3.15 Interim analysis

No formal interim analysis is planned. One interim statistical analysis will be done after completing Phase I part of the study. The final analysis will be after completing Phase II of the study.

4 Sample size calculation

Phase I: In the phase I of the study, there will be 3-6 patients per dose level cohort (for a total of 3 cohorts). A RP2D will be based on safety profile of the dose escalation (cohort A&B) and the dose de-escalation (cohort C). RP2D will be defined as the optimal dose level at which 33%

or less experience DLTs. Thus, including confirmation, at least 3-6 patients will be required for Phase I for each cohort.

Phase II: The sample size is based on an exact test for single proportion to test the null hypothesis $H_0: p \leq 0.10$ where p is the clinical benefit rate in 24 weeks. If the true rate is $p \geq 30\%$, then with one-sided alpha level of 0.05% and a power of 80%, a minimum of approximately 60 (30 per group) evaluable patients are required for the study.

Including dropout rate of 10%, to get 60 evaluable patients, a total of approximately 66 patients (33 patients per group) will be enrolled for the phase 2 of the study for each group (group 1 and group 2). Thus, if fewer than 8 patients show clinical benefit at 24 weeks out of 33 patients within each group then the study will not show significant clinical benefit. Thus, approximately at least 66 patients (33 patients per group (group 1&2)) will be required to be enrolled for the Phase II of the study.

So far 46 patients for group 1 and 33 patients for group 2 are recruited for phase 2.

5 Change to protocol specified analyses

None

6 Appendix

6.1 Imputation rules

6.1.1 Study drug

In the calculation of treatment exposure duration, if a dosing record has either a missing end date (for the last record for that treatment component) or an end date after the cut-off date, the cut-off date will be used as the end date. Such imputed data will be flagged in the listings. Where a date is recorded as a partial date, the missing day will be imputed as follows:

Start date: The day will be imputed by the 15th of the month. If day and month are missing day and month will be imputed by July 1st of the year. If there is a record indicating that the dose record started earlier, the start date will be imputed by the end date of the previous record + 1 day. In case the imputed start date is later than the complete end date, the record will not be considered for analysis.

End date: The day will be imputed by the 15th of the month, and if day and month are missing then by July 1st of the year. If there is a record indicating that this started later, the end date will be imputed by the start date of the next record - 1 day. In case the imputed end date is earlier than the complete start date, the record will not be considered for analysis.

Imputed DAR start and end dates will be flagged in the listings.

The protocol allows for continuous dosing record entry with start dates and end dates for all compounds of study treatment. A separate dosing record should be entered whenever there is a

change in the dosing which can be due to dose change, delay or missed doses. If the start date and end date is on the same date then that DAR record will be called single dose DAR record.

For dates known to be within the trial period, the last known contact date will be used if this imputation makes the date later than the last known contact date but within the trial completion date. If the imputed date is earlier than the first medication date, the first medication date will be used.

For dates prior to the treatment start, the treatment start date will be used if this imputation makes the date later than the treatment start date.

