7.1.2 Treatment period

During the treatment period, the patient must follow the Investigator's instructions with regards to contraception, concomitant medications, and dosing regimen (see [Section 6](#)). Patients will be treated with ribociclib + everolimus + exemestane until disease progression, unacceptable toxicity, withdrawal of consent by the patient, patient is lost to follow up, death, discontinuation from the study treatment due to any other reason or the sponsor terminates the study. For details of assessments, refer to [Table 7-2](#), and [Table 7-3](#).

If a patient remains on study after a dose interruption of >28 days, or after disease progression because the patient had experienced objective evidence of clinical benefit and in the opinion of the investigator it is in the best interest of the patient to remain on study, then this decision and report of a discussion with the sponsor must be reported in the source documentation and in a comment in the eCRF.

7.1.3 End of study treatment visit including safety completion and study treatment discontinuation

Patients who discontinue study treatment should be scheduled for an End of Treatment (EOT) visit within 15 days following the date study treatment is permanently discontinued, at which time all of the assessments listed for the EOT visit will be performed. For details of assessments, refer to [Table 7-1](#). If the decision to withdraw the patient occurs at a regularly scheduled visit, that visit may become the EOT visit rather than having the patient return for an additional visit.

An End of phase disposition eCRF page should be completed, giving the date and reason for stopping the study treatment. If a withdrawal occurs, or if the patient fails to return for visits, the investigator must determine the primary reason for a patient's premature withdrawal from the study and record this information on the EOT eCRF page. The EOT visit is not considered the end of the study.

At a minimum, all patients who discontinue study treatment, including those who refuse to return for a final visit, will be contacted for safety evaluations during the 30 days following the last dose of study treatment.

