2.1.1.9 Last contact date

The last contact date will be derived for patients not known to be dead at the analysis cut-off using the last complete date among the following:

- All assessment dates (e.g. vital signs assessment, performance status). Note, only a true on study assessment date or patient contact date will be used. If there is a visit date without evidence of any actual assessment performed that date will not be used. No dates post cut-off will be used.
- Medication dates including study medications, concomitant medications, and anti-neoplastic therapies administered after study treatment discontinuation (with non-missing medication/procedure term).
- Adverse event dates (with non-missing verbatim AE term present).

- Last known date patient alive collected on the ‘Survival information’ eCRF.
- Date of discontinuation from end of treatment page and ‘End of post-treatment follow-up’ eCRF.

The last contact date is defined as the latest complete date from the above list or the cut-off date whichever comes first. The cut-off date will not be used for last contact date, unless an actual assessment or patient contact was performed.

Important note: imputed dates (e.g. the analysis cut-off date programmatically imputed to replace the missing end date of a dose administration record) will not be used to derive the last contact date, except for the following: partial date’s imputation is allowed to be used for event (death) and for censoring date only if coming from Survival Information page.

The last contact date will be used for censoring of patients in the analysis of overall survival.

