3.2 Treatments (study treatment, rescue medication, concomitant therapies, compliance)

3.2.1 Study treatment exposure

The following algorithm will be used to calculate the duration of study treatment exposure (in cycles and in days) for patients who takes at least 1 dose of the study treatment:

- Duration of exposure (days) to investigational drug = date of last administration of the study drug – date of first administration of the study drug + 1.

- Duration of exposure (days) to study treatment = (latest of last dates of exposure to study treatment (ribociclib, everolimus and exemestane)) – (date of first administration of study treatment (ribociclib, everolimus and exemestane)) + 1.

For patients who did not take any drug, the duration of drug exposure is by definition equal to zero.

- Cumulative Dose: Cumulative dose is defined as the total dose given to a patient during the study treatment. For patients who did not take any drug the actual cumulative dose is by definition equal to zero.
- Average Daily Dose: It is defined cumulative dose divided by the number of days the patients took the drug (excludes the no-dose period)
- Dose Intensity (DI): DI is defined as the ratio of cumulative dose and the number of days the patient should have taken the drug (includes the no-dose period).
- Planned dose intensity (PDI): PDI is defined as the ratio of total planned dose and the number of days the patient should have taken the drug [(planned dose * (last dose date – first dose date+1))].
- Relative Dose Intensity (RDI): RDI is defined as the ratio of dose intensity (DI) and planned dose intensity (PDI) based on planned dose and planned duration, expressed as percentage.

Cumulative Dose, average daily dose, DI, PDI and RDI will be calculated separately for each of the component of study treatment.

Additionally, prior duration of CDK4/6 against the duration of CDK4/6 during the study will be summarized by 25th, 50th (median) and 75th Percentiles of duration.

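### A blank end date on the last dosing record runs to the cut-off, limited at most by last contact and never by treatment stop or death, so exposure can be counted after treatment ended

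*SAP*

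**What the plan says.** SAP 6.1.1 covers dosing records used to calculate exposure duration. Its first rule for filling in end dates reads: "missing end date (for the last record for that treatment component) or an end date after the cut-off date, the cut-off date will be used". Imputed dates are flagged in the listings. The section does not ask whether treatment is ongoing, and it mentions neither the treatment-stop date nor the date of death.

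Near its end, the section has a limiting clause. It opens with "For dates known to be within the trial period" and says that "the last known contact date will be used if this imputation makes the date later than the last known contact date".

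Last contact is defined in SAP 2.1.1.9, mainly for censoring overall survival: "The last contact date will be derived for patients not known to be dead at the analysis cut-off". Its sources go beyond the treatment period. They include antineoplastic therapy given after discontinuation, the end of post-treatment follow-up page, and "Last known date patient alive collected on the" survival page. Imputed dates are excluded, and the example given is "the analysis cut-off date programmatically imputed to replace the missing end date of a dose administration record". So the SAP expects open dosing records, and the limit is not circular.

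The date that is needed is already collected. Protocol 7.1.3 requires a disposition page "giving the date and reason for stopping the study treatment".

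SAP 3.2.1 computes exposure as last minus first administration date plus one. For the triplet it takes the "latest of last dates of exposure to study treatment". Cumulative dose, dose intensity and RDI are defined in the same section.

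**The concern.** Running an open record to the cut-off is right for a patient who is still taking the drug. For a patient who has stopped, it adds days at the last recorded dose that were never taken. The last-contact limit, where it applies, brings the date forward but does not bring it back to treatment stop. Protocol follow-up continues after discontinuation, every 8 weeks for efficacy (7.1.7) and every 24 weeks for survival (7.1.8), so last contact can fall months after the last dose.

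The summaries at stake are exposure duration, cumulative dose, dose intensity and RDI by Phase I cohort and Phase II group (SAP 3.2 and 3.8.4.5). Two other displays also rest on treatment duration: on-study against prior CDK4/6 inhibitor duration (SAP 3.2.1) and treatment length in the swimmer plot (SAP 3.7.2.2). Against the true stop date, the error in duration can only be upward.

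**Working it through.** The plan states no figure for this point, so there is none to reproduce. The check compares the end-date rules and then works two illustrations. All patient dates are assumptions.

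**1. End-date rules within SAP 6.1**

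| Rule | Upper limits named |
|---|---|
| Dosing record, 6.1.1 | cut-off; possibly last known contact |
| AE, partial end date, 6.1.2.2 | treatment end + 30 days, month or year end, death, cut-off |
| Concomitant medication, 6.1.3.2 | death, cut-off, end of follow-up |

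Only the dosing rule names neither death nor any date tied to the end of treatment.

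**2. Does the last-contact limit apply?** Two things are left open. The clause concerns dates known to lie within the trial and follows the partial-date rules, so it is not stated whether it covers a wholly missing end date already set to the cut-off. And SAP 2.1.1.9 derives no last contact date for a patient known to be dead.

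**3. A patient who died.** Assume first dose day 1, stop day 60, death day 120, cut-off day 500. Group sizes are from SAP Section 4 (Group 1: 46; Group 2: 33). Duration = last − first + 1. Shift in the group mean = (counted − 60)/n.

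- True: 60 days.
- Limit applies and last contact is no later than death: at most 120 days. Shift at most (120 − 60)/33 = 1.8 days, or (120 − 60)/46 = 1.3 days.
- Limit does not apply: 500 days. Shift (500 − 60)/33 = 13.3 days, or (500 − 60)/46 = 9.6 days.

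**4. A discontinued survivor.** Assume 300 mg/day planned, stop day 112, cut-off day 400, last record open. Dose intensity = cumulative dose / days including no-dose periods; RDI = dose intensity / 300.

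- Reduced patient: 300 mg on days 1–56, then 250 mg. At true stop: (56×300 + 56×250)/112 = 30,800/112 = 275 mg/day, so RDI is 91.7%.
- Interrupted patient: 300 mg on days 1–56, none on days 57–84, then 300 mg. At true stop: (56×300 + 28×300)/112 = 25,200/112 = 225 mg/day, so RDI is 75.0%.

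| End date used | Exposure (days) | Cumulative dose, reduced (mg) | RDI, reduced | Cumulative dose, interrupted (mg) | RDI, interrupted |
|---|---|---|---|---|---|
| True stop | 112 | 30,800 | 91.7% | 25,200 | 75.0% |
| Last contact day 142 | 142 | 38,300 | 89.9% | 34,200 | 80.3% |
| Last contact day 280 | 280 | 72,800 | 86.7% | 75,600 | 90.0% |
| Cut-off day 400 | 400 | 102,800 | 85.7% | 111,600 | 93.0% |

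SAP 3.8.4.5 groups RDI as below 0.7, 0.7 to below 0.9, and 0.9 or more. The reduced patient falls out of the top category already at day 142. The interrupted patient enters it at day 280.

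**The case against.** A reader might infer that every patient who stopped or died is carried to the cut-off. The documents do not support that. The rule acts only on records still lacking an end date at analysis, and the same section has a last-contact limit. Protocol 14.2.25 describes last contact as the last date the patient was known to be alive, which cannot fall after death. On that reading the assumed death case gives at most 120 days, not 500. The SAP is unclear for patients who died; it does not say that they are dosed to the cut-off.

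Open records in stopped patients should also be few. Doses and dose changes go on the dosing record, discontinuation requires a disposition page and registration in the response system, and missing values are queried before lock (Protocol 6.1, 7.1.3, 9.4). Most records still open should belong to patients on treatment, for whom the rule is right. Exposure and dose intensity are descriptive, medians and quartiles are shown beside means, and no test or success criterion uses them.

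All of this limits the size. It does not remove the error: the limit is tied to contact rather than to treatment, it is undefined for patients known to be dead, and flagging a listing does not correct a summary table.

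**Conclusion.** The point holds in limited form. Followed as written, SAP 6.1.1 overstates exposure and cumulative dose for a discontinued patient whose last record is open, by an amount that depends on whether the last-contact limit applies. The two readings of the death case differ more than sevenfold in the mean shift (1.8 against 13.3 days; 1.3 against 9.6), so the ambiguity is worth removing. These figures rest on assumed dates and a single affected patient. The documents do not give the number of open records.

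It would also be wrong to infer that RDI is always pushed toward the planned dose, or that one regimen is favoured. RDI fell for the reduced patient and rose for the interrupted one, and nothing in the documents shows in which group open records would arise. The effect is confined to descriptive exposure and tolerability summaries. The primary clinical benefit rate is untouched.

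**What to change.** Replace the first rule in SAP 6.1.1 with a conditional one:

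- If the patient is ongoing at the cut-off (no end-of-treatment disposition and no death), set a missing end date on the last record to the cut-off.
- Otherwise, set it to the earliest of the recorded date of stopping study treatment, the date of death and the cut-off.
- Flag the imputed date in the listings, as already planned.

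Name the disposition field to be used, and state that it holds the date treatment stopped rather than the date of the end-of-treatment visit. Protocol 14.2.25 defines the date of discontinuation as that visit, and Protocol 7.1.3 allows it up to 15 days after stopping, so using it would leave a small overcount.

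The cost is a sentence or two in the SAP and a small change to the exposure program. No new data are needed.

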6.1.2.2 AE End Date Imputation

Rules for imputing the AE end date:

- Rules for imputing the AE end date:
- If AE day is missing but year and month are available, then the AE end date is set to minimum of (end date of follow-up period (treatment end date + 30 days), last day of the month, date of death, cutoff date).
- If AE month and day are missing but year is available, then it is set to minimum of (end date of follow-up period, Dec-31 of the year, date of death, cutoff date).
- If AE year is missing the end date will not be imputed.
- If complete (imputed) AE end date is available and the imputed AE start date is greater than the (imputed) AE end date, then imputed AE start date should be set to the (imputed) AE end date. If patient has not yet started study treatment, no imputation will be done for AE end date.

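### SAP 6.1.1 drops a dosing record when its mid-point imputed date crosses its own complete date, which understates cumulative dose for that drug

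*SAP*

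**What the plan says.** SAP 6.1.1 uses one mid-point for both ends of a dosing record. If only the day is missing: "The day will be imputed by the 15th of the month". For start dates it adds: "If day and month are missing day and month will be imputed by July 1st of the year"; end dates get the same 1 July. Two exclusion sentences follow. For a partial start date: "In case the imputed start date is later than the complete end date, the record will not be considered for analysis". For a partial end date: "In case the imputed end date is earlier than the complete start date, the record will not be considered for analysis".

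The same section contains rules that limit the damage. Where an adjoining record is informative, "the start date will be imputed by the end date of the previous record + 1 day" and, for the other end, "the end date will be imputed by the start date of the next record - 1 day". There is also a floor: "If the imputed date is earlier than the first medication date, the first medication date will be used". Imputed dates are capped at last contact. The SAP does not say which of these rules comes first when an exclusion sentence also applies. A drug's last record with no end date is kept and closed at the cut-off.

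Other date types are treated differently. In SAP 6.1.2.2, when an adverse event's imputed start passes its end, "then imputed AE start date should be set to the (imputed) AE end date". A partial event end date goes to the end of the month or year, limited by death, cut-off and the end of follow-up. SAP 6.1.3.2 likewise resolves a reversed concomitant-medication pair by moving a date. Neither section deletes the record.

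**The concern.** Take a record that starts on an unknown day in March and ends on 10 March. It is a valid record of 1 to 10 dosing days. The rule imputes 15 March, finds the start after the end, and removes the record. Nothing in the data is inconsistent; the clash exists only because the 15th was chosen.

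There is also an odd ordering. A last record whose end date is wholly missing is kept to the cut-off, while one whose end month is known can be deleted. Less information leads to more retained exposure.

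Dosing records feed exposure duration, cumulative dose, dose intensity (DI) and relative dose intensity (RDI) for each of the three drugs (SAP 3.2.1 and 3.8.4.5). They also supply the first and last administration dates (SAP 2.1.1.2 to 2.1.1.5), on which the on-treatment window (2.1.1.8) and the 30-day limit for best overall response (3.3.1.6) depend.

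**Working it through.** The plan gives no figure for this rule, so there is none to reproduce. The check applies the SAP 6.1.1 rules by date arithmetic.

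**1. Which records can be lost.** With only the day missing, an artefactual clash needs start and end in the same month; a record that spans months cannot clash.

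- Missing start day: dropped if the record ends on days 1 to 14, so at most 14 dosing days are lost.
- Missing end day: dropped if the record starts on day 16 or later, so at most 16 days are lost (16th to 31st).
- Day and month missing, start: dropped if the end is 30 June or earlier, at most 181 days (1 January to 30 June, non-leap year).
- Day and month missing, end: dropped if the start is 2 July or later, at most 183 days (2 July to 31 December).

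**2. How much of the same-month date space this covers.** A 30-day month has 30 × 31 / 2 = 465 pairs with start ≤ end.

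- End day below 15: 14 × 15 / 2 = 105, and 105/465 = 22.6%.
- Start day above 15: 15 × 16 / 2 = 120, and 120/465 = 25.8%.
- Over a full 365-day year: 1,260/5,738 = 22.0% and 1,523/5,738 = 26.5%.

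These are shares of possible date pairs before the neighbouring-record rules. They are not expected rates of deletion.

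**3. Effect on the exposure measures.** From SAP 3.2.1, with a constant planned daily dose, RDI = cumulative dose / (days from first to last dose × planned daily dose). The planned dose is 300 mg ribociclib (Group 1, SAP 1.1) and the reduced dose is 50 mg lower (Protocol Table 6-5). The dates are assumed: 300 mg from 1 January to 19 March 2018 (78 days), then 250 mg from 20 March with the end recorded only as March, true end 31 March (12 days). The imputed end, 15 March, precedes 20 March, so the second record is dropped.

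| Handling | Cumulative dose (mg) | Days | RDI |
|---|---|---|---|
| Truth | 78×300 + 12×250 = 26,400 | 90 | 97.8% |
| Deleted, window ends at last retained dose | 23,400 | 78 | 100.0% |
| Deleted, window kept at 90 days | 23,400 | 90 | 86.7% |
| Kept, end set to the known start | 23,650 | 79 | 99.8% |
| Kept, end set to month end | 26,400 | 90 | 97.8% |

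Deletion always lowers cumulative dose, here by 3,000 mg. RDI can rise or fall, depending on whether the denominator shrinks with the record. If the last record had been at 300 mg and the window shrank, RDI would stay at 100% although 12 days and 3,600 mg were lost. With the window kept, 86.7% would also move the patient from the top RDI category of SAP 3.8.4.5 (≥0.9) to the middle one.

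**4. An upper-end case.** Suppose 300 mg from 1 January to 1 July (182 days), then 250 mg from 2 July with only the year of the end known, true end 31 December (183 days). The truth is 54,600 + 45,750 = 100,350 mg over 365 days, RDI 91.6%. Deletion leaves 54,600 mg: RDI 100.0% over 182 days, or 49.9% over 365.

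**The case against.** The strongest reply is that the rule will seldom act and seldom matter. Interior records can usually be dated from their neighbours. Protocol 9.4 provides for queries on missing values before lock. On pharmacokinetic sampling days, which include Cycle 1 Day 1 for patients with recent CDK4/6 inhibitor treatment, dosing is supervised in the clinic and its date and time must be recorded (Protocol 6.2.4.1, 7.2.3.1.1 and 7.2.3.1.2), so a partial first-dose date should be rare. All of that stands, and it is why the point is minor.

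Two further objections also stand. Not every clash is an artefact: a start recorded in April with a complete end of 10 March conflicts on any day, and keeping that record as a valid dose would be wrong. And simply moving the imputed date to the known date recovers little: 250 of the 3,000 mg lost in the example.

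It is also true that the adverse-event rule is not an exact parallel, since the end date it moves to may itself be imputed. What remains is that those rules move a date and keep the record.

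One defence does not stand. Collected data are listed and imputed dates flagged, but a record shown in a listing is still absent from the summaries.

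**Conclusion.** The point holds, at minor size. When the partial date is compatible with the complete one, SAP 6.1.1 discards a documented dose because of its own imputation. Cumulative dose for that drug is understated; exposure duration is understated if the record is at the start or end of treatment. The number of partial dosing dates is not given, so the total bias cannot be estimated; that it is probably small is a judgement.

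A reader might infer more than the documents support:

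- **That dose intensity falls.** The direction is not fixed, as the example shows.
- **That study day 1, the on-treatment window and the start of PFS and OS shift.** SAP 2.1.1.4 and 2.1.1.5 take the first and last non-zero dose of any component. Treatment-level dates, and with them the 30-day best-response limit, are affected only if no other drug has a record reaching the same date.
- **That about a quarter of partial records would be deleted.** The 22.6% and 25.8% assume equally likely same-month pairs and ignore the neighbouring-record rules.
- **That the primary analysis loses patients.** The full analysis set (SAP 2.2.1) requires a dose of each component to have been taken; nothing there makes a deleted exposure record count as a dose not taken. SAP 6.1.1 introduces its rules for calculating exposure duration. Clinical benefit rate is not directly affected.

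**What to change.** Replace both exclusion sentences in SAP 6.1.1 with:

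> Apply the neighbouring-record rule first. If the imputed start date is still after the complete end date, set it to the latest of the first day of the recorded month (or year, if the month is missing), the previous record's end + 1 day, and the first medication date. If the imputed end date is still before the complete start date, set it to the earliest of the last day of the recorded month (or year), the next record's start − 1 day, the last contact date, the date of death and the cut-off date. Keep and flag the record. Query a record, and exclude it if unresolved, only when the recorded month or year itself contradicts the complete date.

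The month-end choice for end dates matches what SAP 6.1.2.2 and 6.1.3.2 already do. The text should add that the first medication date is taken from records with complete dates, so that the rule is not circular when the first record is the partial one.

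The cost is two sentences and minor programming. The downside is possible overstatement of a retained record. With only the day missing it is at most 15 days (start and true end on the 16th, closed on the 31st: 16 − 1), and 11 days in the example if the drug had truly stopped on 20 March. For a year-only date it could be larger and depends on the other bounds, so such records should be queried before lock.
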